### 8.3.4 Clinical Laboratory Assessments

- Refer to Appendix 2 for the list of clinical laboratory tests to be performed and to the SoA for the timing and frequency.

- The investigator must review the laboratory report, document this review, and record any clinically relevant changes occurring during the study in the AE section of the case report form (CRF). The laboratory reports must be filed with the source documents. Clinically significant abnormal laboratory findings are those which are not associated with the underlying disease, unless judged by the investigator to be more severe than expected for the participant's condition.
- All protocol-required laboratory assessments, as defined in Appendix 2, must be conducted in accordance with the operations/laboratory manual and the SoA.
- If laboratory values from nonprotocol specified laboratory assessments performed at the institution's local laboratory require a change in study participant management or are considered clinically significant by the investigator (eg, SAE or AE or dose modification), then the results must be recorded in the appropriate CRF (eg, SLAB).
- For any laboratory tests with values considered clinically significantly abnormal during participation in the study or within 30 days after the last dose of study intervention, every attempt should be made to perform repeat assessments until the values return to normal or baseline or if a new baseline is established as determined by the investigator.

#### **8.3.4.1 CMV IgG Testing**

For stratification, serum CMV IgG will be assessed by Enzyme immunoassay and the participant will be determined whether the serum is IgG (+) or IgG (-) at screening visit (Visit 1).

#### **8.3.4.2 CMV PCR Testing**

Plasma, swab from injection-site and adhesive tapes (inside and outside, respectively), urine and saliva will be collected from all participants at time points specified below and Appendix 2.

DNA will be extracted from each samples and assayed for the presence of CMV by a PCR assay. If CMV is detected, distinction between V160 vaccine virus and non-vaccine virus will be performed in a separate PCR assay, except swab samples.

Refer to Appendix 2 for a summary of the CMV PCR assay.

##### **8.3.4.2.1 Plasma**

Plasma samples will be collected at 3 points on Day 1 (prior to vaccination, 0-min and 3-hour post vaccination), and each 1 point on Day 3, 7, and 14 as shown in Appendix 2 in order to evaluate biodistribution of V160 in the human body. Blood will be drawn from the other arm from the vaccinated arm at the time point of just after vaccination on Day 1.

### **8.3.4.2.2      Swab**

Swab samples will be collected at 4 points on Day 1 (0-min, 10-min, 20-min and 30-min post vaccination) from injection-site, and 3 points on Day 1 (10-min, 20-min and 30-min post vaccination) from adhesive tapes (inside and outside, respectively) as shown in Appendix 2, in order to evaluate viral leakage from injection-site to assess risk for horizontal infection of V160. Injection-site will be covered with an adhesive tape just after vaccination (after swab sampling from injection-site), and the adhesive tape will be changed by 10 minutes (after swab sampling from injection-site), ie, at 10 minutes and at 20 minutes after vaccination on Day 1. At 30 minutes after vaccination on Day 1, Month 2 and Month 6, the investigator or delegate should confirm that the injection-site of the participant is no longer bleeding prior to be free from covering with the adhesive tapes.

### **8.3.4.2.3      Urine and Saliva**

Urine and saliva samples will be collected at each visit (7 points prior to vaccination from Day 1 through Month 7) specified in the SoA and Appendix 2 for evaluation of viral shedding.

## **8.4      Adverse Events (AEs), Serious Adverse Events (SAEs), and Other Reportable Safety Events**

The definitions of an AE or SAE, as well as the method of recording, evaluating, and assessing causality of AE and SAE and the procedures for completing and transmitting AE, SAE, and other reportable safety event reports can be found in Appendix 3.

Adverse events, SAEs, and other reportable safety events will be reported by the participant (or, when appropriate, by a caregiver, surrogate, or the participant's legally authorized representative).

The investigator, who is a qualified physician, and any designees are responsible for detecting, assessing, documenting, and reporting events that meet the definition of an AE or SAE, as well as other reportable safety events. Investigators remain responsible for following up AE, SAEs, and other reportable safety events for outcome according to Section 8.4.3.

## **8.4.1      Time Period and Frequency for Collecting AE, SAE, and Other Reportable Safety Event Information**

All AEs, SAEs, and other reportable safety events that occur after the consent form is signed but before allocation/randomization must be reported by the investigator if they cause the participant to be excluded from the study, or are the result of a protocol-specified intervention, including but not limited to washout or discontinuation of usual therapy, diet, placebo treatment, or a procedure.

From the time of allocation/randomization through 14 days following the first vaccination(s) and from the time of any subsequent vaccination(s) through 14 days thereafter, all AEs, SAEs, and other reportable safety events must be reported by the investigator.

Additionally, any SAE brought to the attention of an investigator at any time outside of the time period specified in the previous paragraph also must be reported immediately to the Sponsor if the event is either:

1. A death that occurs prior to the participant completing the study, but outside the time period specified in the previous paragraph.

OR

2. An SAE that is considered by an investigator who is a qualified physician to be vaccine related.

Investigators are not obligated to actively seek AE or SAE or other reportable safety events in former study participants. However, if the investigator learns of any SAE, including a death, at any time after a participant has been discharged from the study, and he/she considers the event to be reasonably related to the study intervention or study participation, the investigator must promptly notify the Sponsor.

All initial and follow-up AEs, SAEs, and other reportable safety events will be recorded and reported to the Sponsor or designee within the time frames as indicated in [Table 2](#).

Table 2 Reporting Time Periods and Time Frames for Adverse Events and Other Reportable Safety Events

Type of Event	Reporting Time Period: Consent to Randomization/Allocation	Reporting Time Period: Randomization/Allocation through Protocol-Specified Follow-up Period	Reporting Time Period: After the Protocol Specified Follow-up Period	Timeframe to Report Event and Follow-up Information to SPONSOR:
Non-Serious Adverse Event (NSAE)	Report if: - due to protocol-specified intervention - causes exclusion - participant is receiving placebo run-in or other run-in treatment	Report all from the time of each vaccination through 14 days thereafter.	Not required	Per data entry guidelines
Serious Adverse Event (SAE)	Report if: - due to protocol-specified intervention - causes exclusion - participant is receiving placebo run-in or other run-in treatment	Report all for the duration of an individual's study participation.	Report if: - drug/vaccine related. - any death until participant completion of study (Follow ongoing to outcome)	Within 24 hours of learning of event
Cancer	Report if: - due to intervention - causes exclusion	Report all for the duration of an individual's study participation.	Not required	Within 5 calendar days of learning of event
Overdose	Report if: - receiving placebo run-in or other run-in medication	Report all for the duration of an individual's study participation.	Not required	Within 5 calendar days of learning of event

#### 8.4.2 Method of Detecting AEs, SAEs, and Other Reportable Safety Events

Care will be taken not to introduce bias when detecting AEs and/or SAEs and other reportable safety events. Open-ended and nonleading verbal questioning of the participant is the preferred method to inquire about AE occurrence.

#### 8.4.3 Follow-up of AE, SAE, and Other Reportable Safety Event Information

After the initial AE/SAE report, the investigator is required to proactively follow each participant at subsequent visits/contacts. All AE, SAE, and other reportable safety events including cancer, and overdose will be followed until resolution, stabilization, until the event is otherwise explained, or the participant is lost to follow-up (as defined in Section 7.3). In addition, the investigator will make every attempt to follow all nonserious AEs that occur in

randomized participants for outcome. Further information on follow-up procedures is given in Appendix 3.

#### **8.4.4 Regulatory Reporting Requirements for SAE**

Prompt notification (within 24 hours) by the investigator to the Sponsor of SAE is essential so that legal obligations and ethical responsibilities towards the safety of participants and the safety of a study intervention under clinical investigation are met.

The Sponsor has a legal responsibility to notify both the local regulatory authority and other regulatory agencies about the safety of a study intervention under clinical investigation. All AEs will be reported to regulatory authorities, IRB/IECs, and investigators in accordance with all applicable global laws and regulations (ie, per ICH Topic E6 (R2) Guidelines for Good Clinical Practice [GCP]).

Investigator safety reports must be prepared for suspected unexpected serious adverse reactions (SUSARs) according to local regulatory requirements and Sponsor policy and forwarded to investigators as necessary.

An investigator who receives an investigator safety report describing an SAE or other specific safety information (eg, summary or listing of SAE) from the Sponsor will file it along with the IB and will notify the IRB/IEC, if appropriate according to local requirements.

#### **8.4.5 Pregnancy and Exposure During Breastfeeding**

Information in this section is not applicable since participants are males and partner pregnancy/lactation information is not required.

#### **8.4.6 Disease-related Events and/or Disease-related Outcomes Not Qualifying as AEs or SAEs**

There are no disease-related events and/or disease related outcomes not qualifying as AEs or SAEs for this study.

#### **8.4.7 Events of Clinical Interest (ECIs)**

Selected nonserious and SAEs are also known as ECIs and must be reported to the Sponsor. There are no ECIs for this study.

### **8.5 Treatment of Overdose**

In this study, an overdose is defined as receipt of more than 1 dose of study vaccine in a 24-hour period.

Sponsor does not recommend specific treatment for an overdose.

## **8.6 Pharmacokinetics**

PK parameters will not be evaluated in this study.

## **8.7 Pharmacodynamics**

Pharmacodynamic parameters will not be evaluated in this study.

## **8.8 Future Biomedical Research Sample Collection**

If the participant signs the future biomedical research consent, the following specimens will be obtained as part of future biomedical research:

- DNA for future research

## **8.9 Planned Genetic Analysis Sample Collection**

Planned genetic analysis samples will not be evaluated in this study.

## **8.10 Visit Requirements**

Visit requirements are outlined in Section 1.3. Specific procedure-related details are provided in Section 8.

# **9 STATISTICAL ANALYSIS PLAN**

This section outlines the statistical analysis strategy and procedures for the study. Changes to analyses made after the protocol has been finalized, but prior to unblinding, will be documented in a supplemental SAP (sSAP) and referenced in the Clinical Study Report (CSR) for the study. Post hoc exploratory analyses will be clearly identified in the CSR.

## 9.1 Statistical Analysis Plan Summary

Key elements of the statistical analysis plan are summarized below; the comprehensive plan is provided in Sections 9.2-9.12.

Study Design Overview	A Phase I Randomized, Double-Blind, Placebo-controlled Study to Evaluate the Safety, Tolerability and Immunogenicity of V160 (Human Cytomegalovirus Vaccine) in Healthy Japanese Men
Intervention Assignment	Participants will be randomized in a 2:1 ratio to either V160 or Placebo, stratified by CMV serostatus.
Analysis Populations	Efficacy: Per Protocol Immunogenicity (PPI) population Safety: All participants as treated (APaT) population
Primary Endpoint	

Solicited injection site AEs within Days 1 through 5 after each vaccination visit

Solicited systemic AEs within Days 1 through 14 after each vaccination visit

Vaccine-related SAEs within Days 1 through 14 after each vaccination visit

Secondary Endpoint	

CMV-specific NAb titers at 1 month PD3

Viral detection of V160 in plasma, urine and saliva, and injection-site swab and adhesive tape swab

Statistical Methods for Key Efficacy Analyses	CMV-specific NAb GMT at 1 month PD3 will be analyzed for seronegative participants using analysis of variance (ANOVA) model. The model will include term for intervention. The GMT ratio and 95% confidence intervals (CIs) will be estimated from this model.
Statistical Methods for Key Safety Analyses	Incidence of solicited injection site AEs, solicited systemic AEs and vaccine-related SAEs will be summarized for each serostatus, respectively.
Interim Analyses	No interim analyses are planned in this study.
Multiplicity	No multiplicity adjustment is planned in this study.
Sample Size and Power	A total of 9 participants will be enrolled for each CMV serostatus. Assuming a discontinuation rate of approximately 20%, 7 participants are expected to complete intervention.

## 9.2 Responsibility for Analyses/In-house Blinding

The statistical analysis of the data obtained from this study will be the responsibility of the SPONSOR. This study will be conducted as a double-blind study under in-house blinding procedures. The official, final database will not be unblinded until medical/scientific review has been performed, protocol deviations have been identified, and data have been declared final and complete.

### 9.3 Hypotheses/Estimation

There are no hypotheses for the study. Objectives are stated in Section 3.

### 9.4 Analysis Endpoints

#### 9.4.1 Immunogenicity Endpoints

##### Secondary Endpoint

- Geometric mean of CMV-specific NAb titers at 1 month PD3 in initially CMV-seronegative participants

##### Exploratory Endpoints

- Percent Seropositivity (Defined by NAb titer  $\geq$  assay defined cutoff level) at 1 month PD3 in initially CMV-seronegative participants
- Geometric mean of CMV-specific NAb titer at 1 month PD3 in initially CMV-seropositive participants
- Geometric mean of CMV-specific NAb fold-rise at 1 month PD3 relative to Day 1 (GMFR) in initially CMV-seropositive participants

#### 9.4.2 Safety Endpoints

- Solicited injection site AEs within Days 1 through 5 after each vaccination visit, solicited systemic AEs and vaccine-related SAEs within Days 1 through 14 after each vaccination visit
- Viral detection of V160 in plasma, urine and saliva, and injection-site swab and adhesive tape swab

### 9.5 Analysis Populations

#### 9.5.1 Immunogenicity Analysis Populations

##### Per Protocol Immunogenicity (PPI) population

The PPI population will serve as primary immunogenicity analysis. To be eligible for inclusion in the PPI population, study participants must satisfy the following criteria:

- Participants have received all 3 vaccinations within the vaccination visit window specified in the SoA (Section 1.3).
- Have not deviated from protocol in ways that could affect the immune response to vaccination

The final determination of protocol deviations that could affect immune response to vaccination, and thereby the composition of the PPI population, will be made prior to the final unblinding of the database and will be documented in a separate memo.

Participants will be included in the intervention group to which they are randomized for the analysis of immunogenicity. Details on the approach to handling missing data are provided in Section 9.6 Statistical Methods.

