### 2.2.2.2 Clinical Studies

#### Phase 1 Clinical Study

The first-in-human study was a Phase 1 dose ranging study to assess the safety and immunogenicity of various antigen dose levels, formulations, and routes of administration in healthy volunteers 18 years of age and older (V160-001) in United States. In study V160-001, the safety and tolerability as well as the immunogenicity of V160 was evaluated in both CMV seronegative and seropositive participants and is briefly summarized below. Refer to the IB for more detailed information.

Participants in study V160-001 received a 3-dose vaccination regimen (0-1-6 month schedule) at various doses (10-250 units) administered intramuscularly or intradermally, with and without aluminum phosphate adjuvant. A saline placebo was used as the control.

In initially CMV seronegative participants, all vaccination groups receiving V160 with and without aluminum phosphate adjuvant exhibited statistically significant higher CMV-specific NAb titers compared with the placebo group. The NAb geometric mean titer (GMT) at Month 7 was highest in recipients of V160 100 unit dose + aluminum phosphate adjuvant.

Robust cell mediated immune responses were also noted among CMV seronegative participants but no differences across dose groups of V160 were observed. Overall, cell mediated immune responses at all doses, and NAb responses at some doses (including 100U+ aluminum phosphate adjuvant) in CMV seronegative participants approximated those observed in naturally infected CMV seropositive participants.

All tested V160 formulations were safe and generally well-tolerated. No SAEs and no events of clinical interest (ECIs) (overdoses, pre-defined elevated hepatic enzyme, and autoimmune conditions) were reported. Overall, adjuvant-containing formulations were more reactogenic than unadjuvanted irrespective of dose. Across the different vaccination groups, the majority of AEs were the solicited injection site AEs (pain/tenderness, erythema/redness, and swelling) and the solicited systemic AEs (headache, fatigue, muscle pain, and joint pain); all of these events were transient and most were mild to moderate in intensity. No vaccine strain CMV was detected by polymerase chain reaction (PCR) in the saliva or urine of vaccine recipients.

Refer to the IB for further details regarding viral replication, virological characteristics of the vaccine virus, as well as detailed background information on animal studies.

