## 3 HYPOTHESIS, OBJECTIVES, AND ENDPOINTS

There are no hypotheses for the study.

The following objectives will be evaluated in healthy Japanese male participants 20 years to 64 years of age inclusive.

Objectives	Endpoints
Primary	
To assess the safety and tolerability of a 3-dose regimen of V160 administered intramuscular (IM) by cytomegalovirus (CMV) serostatus.	

Solicited injection site adverse events (AEs) within Days 1 through 5 after each vaccination visit, and solicited systemic AEs, and vaccine-related serious adverse events (SAEs) within Days 1 through 14 after each vaccination visit

Secondary	
To evaluate CMV-specific neutralizing antibody (NAb) geometric mean titers (GMTs) at 1 month postdose (PD)3 in initially CMV-seronegative participants vaccinated with a 3-dose regimen of V160 administered IM.	

CMV-specific NAb titers

To evaluate viral detection, viral shedding, and viral leakage of V160 by the number and proportion of the participants with positive viral detection in plasma up to 14 days PD1, in urine and saliva up to 1 month PD3, and in injection-site swab and adhesive tape swab up to 30 minutes PD1 by CMV serostatus.	

Viral detection of V160 in plasma, urine and saliva, and injection-site swab and adhesive tape swab

Exploratory	
To evaluate seroconversion rate based on the NAb titers at 1 month PD3 in initially CMV-seronegative participants vaccinated with a 3-dose regimen of V160 administered IM.	

Seropositivity based on the NAb titers

To evaluate NAb GMT and geometric mean of CMV-specific NAb fold-rise (GMFR) at 1 month PD3 relative to Day 1 in initially CMV-seropositive participants vaccinated with a 3-dose regimen of V160 administered IM.	

CMV-specific NAb titers

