### **9.9 Sample Size and Power Calculations**

Nine participants will be randomized in a ratio of 2:1 into V160 and placebo for each CMV serostatus cohort.

If a specific AE is not observed in any of the 6 participants in V160, then the true incidence of that event is 46% or less with 90% confidence.

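### Seroconversion in the seronegative cohort is defined without the Day 1 neutralizing titer, and natural CMV infection has no place in the GMT analysis

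*Combined protocol and SAP*

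**What the plan says.** **Seroconversion.** The exploratory objective in section 3 is "To evaluate seroconversion rate based on the NAb titers at 1 month PD3 in initially CMV-seronegative participants" who are vaccinated with V160. The matching endpoint in section 9.4.1 begins "Percent Seropositivity (Defined by NAb titer" and asks only for a value at or above the assay cutoff at 1 month after dose 3. Section 4.2.1.1 gives the same definition. Serostatus is set by a screening IgG immunoassay (section 8.3.4.1), up to 21 days before Day 1 (section 1.3). Day 1 NAb is measured in everyone (section 8.2), but its only stated analytic use is the fold-rise in seropositive participants.

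**GMT analysis.** Section 9.6.1 fits an ANOVA to log NAb at 1 month after dose 3 in seronegative participants, with intervention as the only term and observed data only. The per-protocol set in section 9.5.1 requires three in-window doses and that participants "Have not deviated from protocol in ways that could affect the immune response to vaccination". The supportive full analysis set is wider still. Neither mentions natural infection or Day 1 NAb.

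**PCR.** When CMV is detected in plasma, urine or saliva, "distinction between V160 vaccine virus and non-vaccine virus will be performed in a separate PCR assay" (section 8.3.4.2). Section 9.6.2 uses these results for safety tabulations. No section links them to NAb titers.

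**The concern.** Seroconversion is a change of status, and the endpoint measures only where a participant ends up. IgG and NAb are different assays with different cutoffs, so an IgG-negative man can be at or above the NAb cutoff before his first dose. As written, he is credited to the vaccine.

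Natural infection during follow-up raises a related problem. Section 2.2.2.2 reports that "NAb responses at some doses (including 100U+ aluminum phosphate adjuvant) in CMV seronegative participants approximated those observed in naturally infected CMV seropositive participants", so titer alone may not distinguish an infected participant from a vaccine responder. Section 2.2 says infection is asymptomatic in most healthy people, so adverse-event reporting is unlikely to show it. With 3 placebo participants in the stratum, a single such case could change the reported GMT ratio substantially.

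**Working it through.** **Sample size.** Section 9.9: "Nine participants will be randomized in a ratio of 2:1 into V160 and placebo for each CMV serostatus cohort". So the seronegative stratum has 6 V160 and 3 placebo. Section 9.1: "Assuming a discontinuation rate of approximately 20%, 7 participants are expected to complete intervention". Check: 9 × (1 − 0.20) = 7.2, or 7, which agrees. Split 2:1, that is about 4.8 to 2.4, so 5:2 or 4:3 in practice.

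**Seroconversion.** Suppose one of the 6 V160 men is at or above the NAb cutoff on Day 1 and stays there, and k of the other 5 convert. The plan reports (k+1)/6. With a Day 1 condition the rate is k/5. The difference is (5−k)/30.

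| k | As planned (exact 95% CI) | With Day 1 condition (exact 95% CI) |
|---|---|---|
| 5 | 6/6 = 100% (54–100%) | 5/5 = 100% (48–100%) |
| 4 | 5/6 = 83% (36–99.6%) | 4/5 = 80% (28–99.5%) |
| 0 | 1/6 = 17% | 0/5 = 0% |

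The documents do not say how often an IgG-negative man exceeds the NAb cutoff, and they do not give the cutoff.

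**GMT ratio with one infected placebo participant.** Let R be the ratio without infection, and suppose the infected man's log titer covers a fraction f of the distance from the placebo mean to the V160 mean. With nP placebo participants, the placebo log mean rises by f·log(R)/nP, so the ratio becomes R^(1 − f/nP). R and f are assumptions.

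| R | f = 1, nP = 3: R^(2/3) | f = 0.5, nP = 3: R^(5/6) | f = 1, nP = 2: R^(1/2) |
|---|---|---|---|
| 10 | 4.6 | 6.8 | 3.2 |
| 30 | 9.7 | 17.0 | 5.5 |
| 100 | 21.5 | 46.4 | 10.0 |

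**Confidence interval at f = 1.** On the log10 scale the half-width is t × s × √(1/nV + 1/nP). At 6:3 there are 7 df, t = 2.365 and the root is 0.707. Without infection s is the within-group SD. With infection s² = [7·SD² + (log10 R)²·(2/3)]/7. For R = 30, log10 R = 1.477:

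- SD 0.4, no infection: half-width 2.365 × 0.4 × 0.707 = 0.669; 95% CI 6.4 to 140.
- SD 0.4, one infection: s² = (1.12 + 1.455)/7 = 0.368, half-width 1.014; ratio 9.7, 95% CI 0.93 to 100.
- SD 0.2: 13.9 to 65 without infection, 1.4 to 66 with.
- SD 0.4, infected man set aside (6:2): ratio 30, 95% CI 4.8 to 189.

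At 5:2 or 4:3, for R of 10, 30 and 100 and SD of 0.2 and 0.4, every interval with one infection included 1 (lower limits 0.25 to 0.72).

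**Infection in the V160 arm.** An infected man who would not otherwise have responded moves seropositivity from 5/6 to 6/6 and the ratio from R^(5/6) to R. In an existing responder the effect is small: a titer 3 to 10 times the GMT multiplies the ratio by 3^(1/6) = 1.20 to 10^(1/6) = 1.47.

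**Chance of a placebo-arm infection.** The documents give no incidence. For an assumed annual rate r over 7 months, 3 men contribute 3 × 7/12 = 1.75 person-years, and P = 1 − (1 − r)^1.75: 0.9% at r = 0.5%, 1.7% at 1%, 5.2% at 3%.

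**The case against.** The strongest case against is one of weight. Section 9.3 states: "There are no hypotheses for the study. Objectives are stated in Section 3". The primary objective is safety, and the affected results are secondary and exploratory. With so few titers, an outlier would be visible on inspection. Section 9.6.1 leaves exploratory methods to a supplemental SAP, and the endpoint itself is labeled seropositivity; only the objective says seroconversion. All of this stands as a limit on importance. It does not remove the point: the deferral covers methods, while section 9.4.1 already fixes a definition without Day 1, and the secondary GMT ratio is not deferred.

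Some stronger readings are tempting, and the documents do not support them:

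- *The plan would never reveal an infected participant.* Section 9.6.2 tabulates generic and vaccine-type CMV separately, by group and serostatus. A wild-type infection detected in one of 3 placebo men would appear as generic 1/3, vaccine-type 0/3. What is missing is the link to the titers.
- *The samples already collected cleanly separate vaccine response from infection.* Plasma PCR stops at Day 14, and urine and saliva sampling goes from Day 14 to Day 60 to Day 180. A negative PCR does not rule infection out.
- *The collapse of the ratio has a 3–15% chance.* That is the chance of any infection among all 9 men at 0.5–3% per year. The collapse needs a placebo-arm infection.
- *One placebo seroconversion distorts the seroconversion rate.* The section 3 objective concerns V160 recipients, so a placebo infection moves only the GMT ratio.

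Section 2.2.2.2 compares vaccine responses with those of seropositive participants, not with men infected within the previous months. Placing an infected man at the V160 mean is therefore an extrapolation, and the f = 0.5 column shows how far the effect shrinks.

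**Conclusion.** The mismatch between objective and endpoint is plain on the text and does not depend on infection rates. An IgG-negative participant already at or above the NAb cutoff on Day 1 would be counted as a seroconverter. The resulting bias is at most 1/6 for one such man among 6, and small if most of the others respond.

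The infection point is conditional and secondary. It is an unlikely event, about 1–5% for the placebo arm on an assumed incidence range. If it occurs and the titer reaches the V160 mean, it reduces R to R^(2/3) with 3 placebo participants and R^(1/2) with 2. R, the SD, the incidence and the infected man's titer are all assumptions. The change is worth making because it is cheap and because setting aside one of 3 placebo men after unblinding would look driven by the result. The primary safety objective is unaffected.

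**What to change.** 1. In sections 3, 4.2.1.1 and 9.4.1, define seroconversion as Day 1 NAb below the cutoff and NAb at 1 month after dose 3 at or above it. Restrict the denominator to seronegative participants below the cutoff on Day 1.
2. In section 9.6.1 or the supplemental SAP, before unblinding, flag seronegative participants with Day 1 NAb at or above the cutoff, CMV in a Day 1 pre-dose sample, or non-vaccine CMV in plasma, urine or saliva at any visit. List their titers. Show the GMT ratio and seroconversion with and without them as supportive results; the per-protocol result stays primary.
3. State two limits alongside that display. Exclusion on post-randomization infection may be informative, because the vaccine is intended to prevent infection. PCR at discrete visits can miss infections, so an unflagged participant is not proven uninfected.

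The cost is wording, one supportive table and one listing. No new samples or assays are needed, and section 9 already allows documented changes before unblinding. Each flagged participant set aside removes one of very few observations, which is a further reason to keep the display supportive.
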